7.3.3 Further endpoint analyses

Further time-to-event endpoints will be analysed in the same Cox proportional hazards model as the primary analysis.

Change from baseline to 30 days after treatment stop of eGFR (CKD-EPI)_{cr} will be evaluated by an ANCOVA model, including treatment group, gender, geographical region and history of DM as fixed effect and baseline eGFR (CKD-EPI)_{cr} (continuous), age (continuous), LVEF (continuous) as linear covariates.

An unmatched win ratio considering adjudicated CV death and adjudicated HHF will be analysed based on unmatched pairs. All patients randomised to empagliflozin will be compared to all patients randomised to placebo. Only common follow-up time will be considered for the comparison. Patients on empagliflozin are considered to have “won” the comparison if either the other patient has died while the patient on empagliflozin was still alive, or if both patients did not die, then if the other patient had more occurrences of HHF, or if the number of occurrences of HHF is the same but the time to the first occurrence of HHF is longer. The number of comparisons won is noted as N_W . Patients on empagliflozin are considered to have “lost” the comparison if the empagliflozin patient died while the patient on placebo was still alive, or if both patients did not die, then if the patient on empagliflozin had more occurrences of HHF, or if the number of occurrences of HHF is the same but the time to the first occurrence of HHF is shorter. The number of comparisons lost is noted as N_L . The win ratio is N_W / N_L .

The rules for winning and losing follow a modified Rogers 2014 [[R16-4909](#)] approach also considering the time to the first HHF event in case of a tie on the number of HHF events. The analysis of the unmatched win ratio will be conducted as described in Pocock 2012 [[R16-4813](#)].

Further longitudinal continuous endpoints will be analysed in a MMRM, including age, LVEF and eGFR (CKD-EPI)_{cr} at baseline as linear covariates and visit by treatment

Proprietary confidential information © 2019 Boehringer Ingelheim International GmbH or one or more of its affiliated companies

interaction, baseline by visit interaction, geographical region, gender and baseline history of DM as fixed effects.

The details of analyses will be defined in the TSAP prior to unblinding.

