5.1.3 Further endpoints

- Time from first to second adjudicated HHF

Proprietary confidential information © 2019 Boehringer Ingelheim International GmbH or one or more of its affiliated companies

- Time to first all-cause hospitalisation
- Occurrence of adjudicated HHF within 30 days after first adjudicated HHF
- Occurrence of adjudicated HHF and CV death. This endpoint will account for clinical hierarchies in composite outcomes, i.e. CV death is ascribed greater importance than HHF (see win ratio in [Section 7.3.3](#))
- New onset of atrial fibrillation
- Adjudicated MI (fatal or non-fatal)
- Adjudicated stroke (fatal or non-fatal)
- Adjudicated TIA
- Composite of time to first event of all-cause mortality and all cause hospitalisation
- Composite of adjudicated CV death or adjudicated non-fatal MI
- Composite of adjudicated CV death or adjudicated non-fatal stroke
- Adjudicated CV death, adjudicated non-fatal MI, adjudicated non-fatal stroke (3-point MACE)
- Progression to macro albuminuria (defined as UACR >300 mg/g) from baseline for patients with baseline UACR ≤ 300 mg/g
- Time to first new onset of sustained normo- or micro albuminuria (UACR ≤ 300 mg/g) in patients with macro albuminuria at baseline
- Time to first new onset of sustained normo albuminuria (UACR < 30 mg/g) in patients with micro- or macro albuminuria at baseline
- eGFR (CKD-EPI)_{cr} change from baseline to 30 days after treatment stop
- Composite of sustained reduction of ≥40% eGFR (CKD-EPI)_{cr} or sustained eGFR (CKD-EPI)_{cr} <15 mL/min/1.73 m² (< 10 mL/min/1.73 m² for patients with eGFR (CKD-EPI)_{cr} < 30mL/min/1.73 m² at baseline), or adjudicated CV death
- Composite of sustained reduction of ≥40% eGFR (CKD-EPI)_{cr} or sustained eGFR (CKD-EPI)_{cr} <15 mL/min/1.73 m² (< 10 mL/min/1.73 m² for patients with eGFR (CKD-EPI)_{cr} < 30mL/min/1.73 m² at baseline), or all-cause mortality
- Composite of sustained reduction of ≥40% eGFR (CKD-EPI)_{cr} or sustained eGFR (CKD-EPI)_{cr} <15 mL/min/1.73 m² (< 10 mL/min/1.73 m² for patients with eGFR (CKD-EPI)_{cr} < 30mL/min/1.73 m² at baseline), adjudicated CV death, or adjudicated HHF

Proprietary confidential information © 2019 Boehringer Ingelheim International GmbH or one or more of its affiliated companies

- Change from baseline in KCCQ overall summary score at week 52
- Change from baseline in KCCQ total symptom score at week 52
- Change from baseline in KCCQ individual domains at week 52

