7.3.1 Primary endpoint analyses

The primary endpoint will be evaluated on the randomised set using a Cox proportional hazards model with treatment, age (continuous), gender, geographical region, baseline status of DM (DM, pre-DM, no DM), LVEF (continuous) and eGFR (CKD-EPI)_{cr} at baseline (continuous) as covariates.

The time to the event of interest will be computed as (event date – randomisation date) + 1. All events observed after randomisation until completion of the planned treatment phase will be included in the analysis. Patients who do not have an event will be censored at the individual end of the planned treatment phase or the last day that the patient was known to be free of the event, whichever is earlier. The time to censoring will be computed as (individual end of the planned treatment phase or the last day known to be free of the event – randomisation date) + 1. For patients who have more than one primary endpoint event during the trial, the time to the first occurrence of the primary endpoint event will be considered for the primary analysis. Only the adjudicated and confirmed events will be used for the primary analysis.

Proprietary confidential information © 2019 Boehringer Ingelheim International GmbH or one or more of its affiliated companies

To detect any heterogeneity in the treatment effect among diabetic patients, pre-diabetic patients and non-diabetic patients, a subgroup analysis will be performed by including the diabetic status by treatment interaction term into the Cox model.

Standard subgroup analyses of the primary endpoint include geographical region, sex, BMI, LVEF, renal function, prognostic factors, age, ethnicity, race and different background therapies etc. More details will be specified in the TSAP.

A sensitivity analysis will be provided based on the TS only including any events up to 30 days after treatment discontinuation.

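### The Cox model fixed for the two time-to-sustained-albuminuria-regression endpoints omits baseline UACR: the test is valid, but less efficient than the collected data allow

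*Protocol*

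**What the plan says.** Protocol section 5.1.3 lists three albuminuria class-change endpoints among the further endpoints. Two are worded as times to event:

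- Regression to normoalbuminuria: "Time to first new onset of sustained normo albuminuria (UACR < 30 mg/g) in patients with micro- or macro albuminuria at baseline"
- Regression from macroalbuminuria: "Time to first new onset of sustained normo- or micro albuminuria (UACR ≤ 300 mg/g) in patients with macro albuminuria at baseline"

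The third is worded differently, with neither a time-to-event phrase nor a requirement that the change be sustained: "Progression to macro albuminuria (defined as UACR >300 mg/g) from baseline for patients with baseline UACR ≤ 300 mg/g".

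Section 7.3.3 fixes the model: "Further time-to-event endpoints will be analysed in the same Cox proportional hazards model as the primary analysis". Section 7.3.1 lists the covariates that accompany the treatment term: "age (continuous), gender, geographical region, baseline status of DM (DM, pre-DM, no DM), LVEF (continuous) and eGFR (CKD-EPI)_{cr} at baseline". Baseline UACR is not among them, and no other section adds it for these endpoints.

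The Flow Chart schedules UACR at Visits 1 and 2. Section 7.3 defines baseline for endpoints not based on creatinine as the last measurement before the start of trial medication. Section 7.6 does not stratify on UACR.

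**The concern.** For a threshold-crossing endpoint, the starting value largely determines who crosses. Regression to below 30 mg/g is open to everyone who starts at 30 mg/g or above. With the other covariates equal, the planned model gives a patient who starts at 31 mg/g and one who starts at 3000 mg/g the same hazard of reaching the target.

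The protocol does otherwise for neighbouring kidney analyses:

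- The MMRM for longitudinal endpoints carries each endpoint's own baseline: "baseline by visit interaction, geographical region, gender and baseline history of DM as fixed effects".
- The ANCOVA for post-treatment eGFR carries baseline eGFR.
- The eGFR slope model carries baseline eGFR and, since Amendment 3, its interaction with time.
- Endpoints defined by eGFR thresholds are adjusted for their own baseline, because eGFR is in the common Cox model.

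The two UACR regression endpoints are not adjusted for theirs. At stake is efficiency: a wider relative uncertainty, and a hazard ratio that answers a less conditional question, for exploratory endpoints whose main predictor is already in the database.

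**Working it through.** **The plan's own figures.** The protocol gives no event count or power for the albuminuria endpoints. Its primary figure reproduces and is unaffected. The Schoenfeld formula, 4 × (1.960 + 1.282)² / (ln 0.80)², gives 845 events against the stated 841, and 841 events give 89.9% power. Uniform accrual over 18 months plus 20 months of follow-up, with placebo hazard −ln 0.9 per year, gives 4125 patients against 4126.

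**Inputs for the albuminuria check.** From the protocol: the 30 and 300 mg/g thresholds, the visit weeks, 1:1 allocation and two-sided 0.05. Assumed, because the documents do not give them: the UACR distribution, the within-patient variability and the drug effect. In both sets of runs, sustained was taken as two consecutive scheduled visits.

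**First set of assumptions.** 4126 patients; log-normal UACR with median 25 mg/g and between-patient log SD 1.3, so about 1850 patients start at 30 mg/g or above; visits at weeks 4 to 148; follow-up uniform over 20 to 38 months; 150 to 200 runs per scenario.

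- Regression to below 30 mg/g, 12% UACR reduction: adding log baseline UACR raises power from 68% to 84% (within-patient log SD 0.5) and from 57% to 63% (SD 0.8).
- Regression to below 30 mg/g, 8% reduction: gains of 8 and 3 points.
- Regression from macroalbuminuria (150 to 215 patients): gains from none to 9 points.

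**Second set, run independently.** Regression to below 30 mg/g; 600 or 1500 patients starting at 30 mg/g or above, drawn from a log-normal with median 40 mg/g and between-patient log SD 1.2; visits at weeks 4 to 124; 200 runs per scenario. Both models were fitted to the same simulated data: treatment alone, and treatment plus log baseline UACR. A hazard ratio above 1 means more regression on empagliflozin.

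| Patients | Within-patient log SD | Effect (log units) | HR without | HR with | log HR smaller by | Power without → with | Squared z ratio |
|---|---|---|---|---|---|---|---|
| 600 | 0.4 | −0.1 | 1.29 | 1.38 | 20% | 25.0% → 33.0% | 1.54 |
| 600 | 0.4 | −0.2 | 1.70 | 1.88 | 16% | 77.0% → 89.5% | 1.41 |
| 600 | 0.7 | −0.1 | 1.18 | 1.21 | 10% | 17.0% → 20.5% | 1.25 |
| 600 | 0.7 | −0.2 | 1.37 | 1.44 | 13% | 50.0% → 64.5% | 1.32 |
| 1500 | 0.4 | −0.1 | 1.29 | 1.35 | 16% | 50.0% → 61.5% | 1.42 |
| 1500 | 0.4 | −0.2 | 1.62 | 1.79 | 17% | 97.0% → 99.0% | 1.45 |
| 1500 | 0.7 | −0.1 | 1.19 | 1.21 | 10% | 41.0% → 46.5% | 1.23 |
| 1500 | 0.7 | −0.2 | 1.38 | 1.43 | 11% | 87.5% → 95.0% | 1.27 |

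The log HR column is 1 − ln(HR without) / ln(HR with), from unrounded values. The squared z ratio compares the adjusted with the unadjusted test, so the information lost by omission is 1 − 1/1.23 = 19% to 1 − 1/1.54 = 35%. The hazard ratio per log unit of baseline UACR is about 0.04 to 0.22, which is what makes it the dominant predictor.

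Under no effect, both models rejected in 5% to 7% of runs, compatible with 5% given a simulation error of √(0.05 × 0.95/200) = 1.5 points. The error on each power figure is at most √(0.5 × 0.5/200) = 3.5 points.

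Across both sets, the gain for regression to below 30 mg/g runs from 2 points (97% to 99%) to 16 points (68% to 84%).

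**The case against.** Much of the case on the other side stands, and it sets the limits of the point.

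- **No error in inference.** Under randomisation, a Cox model that omits a prognostic covariate still gives a valid test. A reader might infer that the planned hazard ratio is biased toward 1. The documents do not support that: the difference is non-collapsibility, and the protocol nowhere names the UACR-conditional hazard ratio as its target.
- **Chance imbalance.** A reader might also infer that leaving UACR out of both stratification and model makes the comparison unsafe. Randomisation balances UACR in expectation, and the test's size already allows for chance differences, so this adds no separate defect.
- **Reach.** It is tempting to count all three class-change endpoints. Section 5.1.3 words the third only as "Progression to macro albuminuria (defined as UACR >300 mg/g) from baseline", and the protocol does not say that it is a time-to-event endpoint. It cannot be treated as fixed to this model, and no gain for it is counted here.
- **Size.** The figures rest on assumed inputs. The tabulated runs used treatment alone as the base model. The planned covariates, notably eGFR and diabetes status, may correlate with UACR and recover part of the loss.
- **Weight.** These endpoints lie outside the testing strategy, and change in albuminuria over time is analysed separately with baseline adjustment.
- **Deferral.** Section 7.3.3 also says "The details of analyses will be defined in the TSAP prior to unblinding". That line is general, while the model itself is named in the protocol. A TSAP that followed the protocol would repeat the omission, so this is a stated choice rather than an open detail.

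**Conclusion.** The point holds as an efficiency matter for the two endpoints worded as time to first new onset of sustained regression. Their analysis is valid as planned, with correct type I error, but it gives up information. Under the assumed UACR distributions and effects, the cost for regression to below 30 mg/g is roughly 2 to 16 points of power and a log hazard ratio about 10% to 20% smaller than the UACR-conditional one. For regression from macroalbuminuria the power cost is between nothing and about 9 points. The direction was the same in every non-null scenario for the first endpoint, but the exact size cannot be fixed from the documents. The primary and key secondary analyses, the 841 events and the 4126 patients are untouched. It ranks as a free improvement.

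**What to change.** Before unblinding, add one sentence to section 7.3.3: for the two endpoints of sustained regression of albuminuria, log-transformed baseline UACR (continuous) is added to the covariates of the common Cox model. Extend it to progression to macroalbuminuria only if that endpoint is analysed as time to event. The common model without UACR may be kept as a sensitivity analysis.

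No new data, visits or patients are needed. The only downside is that the covariate list for these endpoints differs from the common model.

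### The win ratio is named for adjudicated CV death then adjudicated HHF, but its win and loss rules in Section 7.3.3 turn on death of unspecified cause

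*Protocol*

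**What the plan says.** Protocol Section 5.1.3 lists the occurrence of adjudicated HHF and CV death as a further endpoint that respects clinical priority, "i.e. CV death is ascribed greater importance than HHF", and refers to the win ratio in Section 7.3.3. The paragraph there opens in agreement: "An unmatched win ratio considering adjudicated CV death and adjudicated HHF will be analysed based on unmatched pairs".

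The rules that score each pair follow. The empagliflozin patient wins "if either the other patient has died while the patient on empagliflozin was still alive, or if both patients did not die" and the other patient then has more HHF or, on equal counts, the earlier first HHF. The empagliflozin patient loses "if the empagliflozin patient died while the patient on placebo was still alive", or on the mirrored HHF comparisons. Neither rule gives a cause of death or mentions adjudication.

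Two more sentences bear on the point: "Only common follow-up time will be considered for the comparison", and, closing the section, "The details of analyses will be defined in the TSAP prior to unblinding". Nothing says what a non-CV death does to a pair.

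**The concern.** The endpoint has one top tier by name and, read literally, another by rule. A patient who dies of a non-CV cause has died and is not still alive, so under the literal rule that patient loses to any partner alive at that time, and HHF is never compared. Under the endpoint as named, that death is not an event, and the pair should be decided on CV death and HHF.

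At stake is which quantity gets reported. The win ratio re-expresses the primary composite (CV death or HHF) with priority for the worse event. If non-CV deaths enter its top tier, it is no longer built from the same events as the primary endpoint. If the choice is made only when the derivation is programmed, it could be challenged as made late.

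**Working it through.** **1. The texts side by side.**

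| Place | Top tier | Second tier |
|---|---|---|
| Section 5.1.3 | CV death | adjudicated HHF |
| Section 7.3.3, lead sentence | adjudicated CV death | adjudicated HHF |
| Section 7.3.3, win and loss rules | death, no cause | HHF, not called adjudicated |

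Elsewhere the protocol keeps the two kinds of death apart. Section 5.1.2 lists time to CV death and time to all-cause mortality separately. Section 7.3.2 models HHF jointly with adjudicated CV death, and all-cause hospitalisation jointly with all-cause mortality.

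**2. A pair that flips.** An empagliflozin patient dies of a non-CV cause at month 10 without any HHF. The placebo patient is alive and had one HHF before then. Under the literal rule, empagliflozin loses at the death tier. With CV death only, and common follow-up ending at month 10, neither had a CV death, HHF counts are 0 against 1, and empagliflozin wins.

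**3. Design figures.** The plan gives no figure for the win ratio, so the design inputs were checked first (Section 7.7: placebo event rate 10%/year, hazard ratio 0.80, 18 months accrual plus 20 months follow-up).
- Events: 4(1.960 + 1.282)² / (ln 0.8)² = 844.1, rounded up to 845, against 841 stated.
- Event probability per arm: 1 − [exp(−λF) − exp(−λ(F+A))] / (λA), with A = 1.5 and F = 20/12 years. For λ = −ln 0.9 on placebo and 0.8λ on empagliflozin, the average over arms is 0.2039.
- Patients: 841 / 0.2039 ≈ 4125, against 4126 stated.

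The plan's figures reproduce.

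**4. Size under the two readings.** The protocol does not split deaths by cause, so the following are assumptions: placebo CV death 4%/year and HHF 8%/year at mean frailty, hazard ratio 0.80 on both, and gamma frailty of variance 1 shared by HHF and CV death. As a plausibility check, the first-year risk of a first primary event is then 1 − 1/(1 + 0.12) = 10.7%, near the plan's 10%.

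For each scenario, 3,000,000 independent pairs were drawn with 20 to 38 months of follow-up. Each pair was scored twice on common follow-up, with tiers death, number of HHF and time to first HHF: once with any death at the top, and once with CV death at the top and non-CV death ending follow-up.

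| Non-CV death/year | Non-CV hazard ratio | Win ratio, any death | Win ratio, CV death only | Decided pairs settled on death, any vs CV only |
|---|---|---|---|---|
| 1% | 1.0 | 1.20 | 1.22 | 48% vs 41% |
| 2% | 1.0 | 1.18 | 1.22 | 53% vs 41% |
| 3% | 1.0 | 1.16 | 1.22 | 58% vs 41% |
| 2% | 1.1 | 1.15 | 1.22 | 54% vs 41% |
| 2% | 0.9 | 1.20 | 1.22 | 53% vs 41% |
| 2% | 0.8 | 1.23 | 1.22 | 52% vs 41% |
| 2% | 0.7 | 1.26 | 1.22 | 52% vs 41% |
| 2% | 0.6 | 1.28 | 1.22 | 51% vs 41% |

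With no effect on any component, both versions give 1.00.

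**5. Which direction is plausible.** Section 1.2.3 reports, from the earlier outcome trial in type 2 diabetes, hazard ratios of 0.68 for all-cause mortality and 0.62 for CV death. On a simple count approximation with a share s of placebo deaths being CV, the non-CV hazard ratio is (0.68 − 0.62s)/(1 − s):
- s = 0.5: (0.68 − 0.31)/0.5 = 0.74
- s = 0.7: (0.68 − 0.434)/0.3 = 0.82
- s = 0.8: (0.68 − 0.496)/0.2 = 0.92

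The shares are assumptions. Set against the table, this range runs from a slightly higher ratio, through no change, to a small fall.

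**The case against.** The strongest defence is that the rules are shorthand. They also drop the word adjudicated before HHF, and nobody would conclude that unadjudicated HHF is meant. The lead sentence names CV death, and the protocol writes all-cause mortality when it means that. This reading is plausible, and it means the text cannot be called an explicit any-death rule. It does not close the gap: a patient dead of a non-CV cause is still not alive, so putting CV death in place of died leaves that condition unresolved. The common follow-up sentence does not say that a non-CV death ends follow-up.

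A second defence is that details are left to the TSAP. That would cover a rule not yet written. Here the win and loss rules are already fixed in the protocol, and they do not match the endpoint's name.

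A reader might infer that the wording necessarily pulls the win ratio towards 1. The documents do not support that. It holds only if the drug affects non-CV death less than CV death, which the protocol does not state, and its own earlier-trial figures leave the direction open. Nor did Amendment 3 create the mismatch: it added the time-to-first-HHF tie-break, and the wording on death is unchanged from the 2016 protocol.

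**Conclusion.** The inconsistency is real and small. Sections 5.1.3 and 7.3.3 name adjudicated CV death, while the scoring rules in 7.3.3 are on unqualified death, so two faithful readings give two win ratios. On the assumed rates (CV death 4%/year, HHF 8%/year, hazard ratio 0.80 on both), the any-death version is lower by about 0.03 to 0.07 when non-CV death is unaffected and occurs at 1% to 3%/year (unrounded, 1.195 to 1.157 against 1.222). At 2%/year it is about equal when the non-CV hazard ratio is 0.8, and higher when it is 0.7 or below. Both size and direction rest on a split of deaths, and an effect on non-CV death, that the protocol does not give.

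The win ratio is a further endpoint outside the testing hierarchy of Section 7.2. Type I error and the primary and key secondary results are not affected.

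**What to change.** In Section 7.3.3, write both rules on the endpoint as named:
- Replace died with had an adjudicated CV death, and still alive and did not die with had no adjudicated CV death, in each case within common follow-up.
- Write adjudicated HHF in the count and time-to-first comparisons.
- State that a non-CV death ends that patient's follow-up, and so the pair's common follow-up.

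An all-cause-death version may be reported as a labelled supportive analysis. That would also show how much the result depends on treating non-CV death as the end of follow-up, which handles a competing death as censoring.

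The cost is a few words and one line of derivation code, settled before unblinding. No new data are needed, since CV death is already adjudicated for the primary endpoint. The downside is that slightly fewer pairs are decided at the death tier.
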